### *3.6.3 Vital Signs*

Vital signs will be measured as specified in the Schedule of Procedures (Appendix A). Vital signs will be collected BID, both times prior to dosing with study drug. On Day 1, vital signs will also be collected at 2, 4, 6, and 8 hours post the morning dose. The BID measurements prior to dosing will be averaged prior to summarization.

Vital signs parameters (heart rate, blood pressure, respiratory rate, temperature, and oxygen saturation) will be listed and summarized using descriptive statistics for each treatment group by visit and timepoint. Change from baseline to each scheduled post-dose time point will also be summarized.

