8.8 Vital Signs

Vital signs will include temperature, heart rate, blood pressure, respiratory rate, and oxygen saturation. Vital signs will be collected BID, both times prior to dosing with ADX-629. On Day 1, vital signs will also be collected at 2, 4, 6, and 8 hours post the morning dose.

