### 3 STATISTICAL METHODOLOGY

#### 3.1 General Considerations

##### 3.1.1 *Analysis Day*

Analysis day will be calculated from the date of first dose of study drug. The day of the first dose of study drug will be Day 1, and the day immediately before Day 1 will be Day -1. There will be no Day 0.

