##### 3.1.3 *Definition of Baseline*

Baseline is defined as the last measurement prior to the first dose of study drug.

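### SAP 3.6.3 averages the two daily pre-dose vital-sign readings, which mixes pre-drug and post-dose values in the Day 1 row and narrows the tabulated extremes, with no by-arm count of abnormal values to offset this

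*SAP*

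**What the plan says.** Protocol 8.8 sets the collection rule: "Vital signs will be collected BID, both times prior to dosing with ADX-629". SAP 3.6.3 repeats it and adds extra readings on the first day: "On Day 1, vital signs will also be collected at 2, 4, 6, and 8 hours post the morning dose". It then adds a step that is not in the protocol: "The BID measurements prior to dosing will be averaged prior to summarization".

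The same SAP section says the parameters "will be listed and summarized using descriptive statistics for each treatment group by visit and timepoint", and "Change from baseline to each scheduled post-dose time point will also be summarized".

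Two general definitions bear on this. SAP 3.1.1 says "The day of the first dose of study drug will be Day 1". SAP 3.1.3 says "Baseline is defined as the last measurement prior to the first dose of study drug". Section 3.6.3 does not mention either, and it does not exempt Day 1 from averaging.

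SAP 3.1.4 includes the minimum and maximum among the descriptive statistics. SAP 3.6.2 plans by-arm counts of abnormal and of clinically significant laboratory results. SAP 3.6.3 plans no such count for vital signs. Protocol 7.1 makes vital signs, including oxygen saturation, a component of the primary endpoint.

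**The concern.** There are two separate problems.

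**Day 1.** Day 1 is the day of first dose, and SAP 3.6.3 itself refers to a morning dose on that day. If that is the first dose, the first pre-dose reading is drug-free and the second follows a dose. Their average describes neither state, yet it would appear as the Day 1 pre-dose row.

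**Other days.** Averaging comes before summarization, so an isolated low saturation or high heart rate is pulled towards the day's other reading before any statistic is computed. The tabulated minimum and maximum are then extremes of averages. In a safety table the isolated excursion is often what the reader is looking for, and no by-arm count of abnormal readings makes up for its loss. Averaging also sits awkwardly with the section's own undertaking to summarise by timepoint, because it merges two of them.

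**Working it through.** The plan gives no figure on this point, so there is none to reproduce. The checks are arithmetic on the rule, comparison with the documents' own cut-offs, and an illustration under stated assumptions.

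**1. The Day 1 row.** Let B be the reading before the first dose and P the reading before the second. The averaged value is (B + P)/2, which differs from B by (P − B)/2. Take B = 96% and P = 92%:

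- The averaged Day 1 value is (96 + 92)/2 = 94%.
- Baseline under SAP 3.1.3 is 96%, because P comes after the first dose and is not eligible.
- With 3.1.3 governing, change to a later 92% is 92 − 96 = −4. Only the Day 1 pre-dose row is mixed.
- If a programmer used the averaged row as baseline, the same change would read 92 − 94 = −2.

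**2. Excursions against the documents' cut-offs.** The cut-offs come from Protocol Appendix E (severe category; shock for systolic pressure). They are severity categories, not safety thresholds set for this analysis. The paired readings are invented examples.

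| Parameter | Cut-off | Two readings | Average | Crossing visible? |
|---|---|---|---|---|
| Oxygen saturation | ≤93% | 91, 97 | 94 | No |
| Heart rate | ≥125 | 130, 112 | 121 | No |
| Respiratory rate | ≥30 | 32, 24 | 28 | No |
| Systolic pressure | <90 | 86, 104 | 95 | No |

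**3. Spread.** For two readings with equal SD and correlation ρ, the SD of the average is √((1 + ρ)/2) times the single-reading SD: 0.87 at ρ = 0.5 and 0.92 at ρ = 0.7.

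**4. Illustration for saturation.** The mean, SD and ρ are assumptions; the documents give none. Treat the two readings as bivariate normal with z = (93 − mean)/SD.

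- P(any reading ≤93) = 2Φ(z) − Φ₂(z, z; ρ)
- P(average ≤93) = Φ(z/√((1 + ρ)/2))
- Share hidden = 1 − P(average ≤93)/P(any ≤93), because an average at or below 93 requires at least one such reading.

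Worked case, mean 95, SD 2, ρ 0.7: z = −1, Φ(z) = 0.1587 and Φ₂ = 0.0840, so P(any) = 0.233. P(average) = Φ(−1/0.922) = 0.139. Share hidden = 1 − 0.139/0.233 = 40%.

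| Mean | SD | ρ | Any ≤93 | Average ≤93 | Gap (points) | Share hidden |
|---|---|---|---|---|---|---|
| 95 | 1.5 | 0.5 | 15.4% | 6.2% | 9.2 | 60% |
| 95 | 1.5 | 0.7 | 14.1% | 7.4% | 6.7 | 47% |
| 95 | 2.0 | 0.5 | 25.5% | 12.4% | 13.1 | 51% |
| 95 | 2.0 | 0.7 | 23.3% | 13.9% | 9.4 | 40% |
| 96 | 1.5 | 0.5 | 4.1% | 1.1% | 3.1 | 75% |
| 96 | 1.5 | 0.7 | 3.8% | 1.5% | 2.3 | 61% |
| 96 | 2.0 | 0.5 | 11.5% | 4.2% | 7.4 | 64% |
| 96 | 2.0 | 0.7 | 10.5% | 5.2% | 5.4 | 51% |

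With readings rounded to whole percentages and capped at 100%, mean 96, SD 1.5-2.5 and ρ 0.3-0.9, the share hidden runs from 36% to 86%. The direction is the same throughout; the size depends on the inputs.

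**The case against.** Several stronger readings are tempting. The documents do not support them.

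*The baseline is contaminated.* SAP 3.1.3 defines baseline for the whole plan, and the averaging sentence concerns summarization only; it does not redefine baseline. What stands is that 3.6.3 leaves the precedence unstated.

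*Any Day 1 drug effect appears at half its size.* The halving applies only to the averaged pre-dose row. The readings at 2, 4, 6 and 8 hours are outside the averaging rule, and each has its own change from baseline.

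*Only a listing would reveal an excursion.* Protocol 8.1 makes clinically significant abnormal findings reportable as adverse events, and SAP 3.6.1 counts these by arm. Need for supplemental oxygen reaches the NIAID score and the related by-arm proportion in SAP 3.4.2. Protocol 8.2 does keep most events of COVID-19 progression out of SAE reporting, but it treats them as captured by the endpoints. What has no by-arm count is a reading judged not clinically significant that led to no oxygen.

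*Averaging breaks the protocol's analysis.* Protocol 9.2.2 promises descriptive summaries at each visit, and one averaged value per visit is compatible with that.

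Three further limits hold. A fall present at both readings survives averaging. Outpatients dose at home and attend on only some days, so they may have one reading at a visit; averaging then changes nothing. The schedule table is not in the available text, so the days with two readings cannot be checked. Finally, the trial has about 30 subjects and is exploratory, so no formal inference is at risk.

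**Conclusion.** The point holds in a limited form. Read as written, the rule mixes a pre-drug and a post-dose value in the Day 1 pre-dose row, provided the first dose is the morning dose and both readings are taken. On other days with two readings it narrows the tabulated spread, minimum and maximum of a primary-endpoint component, and no by-arm abnormality count offsets this.

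The size in this trial is unknown. The 40% to 75% is an illustration under assumed variability. It is conditional on days that contain a low reading, and it counts days, not subjects; as a share of all subject-days the gap is about 2 to 13 percentage points. A reader should not take either range as an estimate for this trial, nor conclude that change from baseline is wrong or that excursions go unreported.

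A change is still worth making before the SAP is finalised: the data are already collected, and it alters what the primary safety tables show.

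**What to change.** 1. Delete the averaging sentence from SAP 3.6.3 and summarise the morning and evening pre-dose readings as separate timepoints. At minimum, exempt Day 1 and baseline from averaging.
2. State in 3.6.3 that baseline follows 3.1.3.
3. Add one by-arm summary of each subject's worst post-baseline value: lowest saturation and systolic pressure; highest heart rate, respiratory rate and temperature. Include the number of subjects with saturation at or below 93%, taken from Appendix E's severe category purely as a descriptive cut-off.
4. Show that summary separately for subjects who were inpatients and outpatients at Screening. Protocol 6.3 gives inpatients ten assessment days in the Treatment Period (Days 1, 4, 7, 10, 13, 16, 19, 22, 25 and 28). Outpatients have five with vital signs (Days 1, 7, 13, 22 and 28; Day 4 is by telephone).

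The cost is SAP wording, slightly longer tables and one new table; no new data are needed. The drawback is that a worst value becomes more extreme as readings accumulate. Splitting by status at Screening reduces this but does not remove it, since discharged inpatients move to the outpatient schedule. The table should therefore also show the number of readings per subject.

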### *3.6.4 Physical Examinations*

Physical examination will be performed as specified in the Schedule of Procedures (Appendix A). All physical examination results will be listed.

### *3.6.5 Electrocardiograms (ECG)*

Twelve-lead ECGs will be performed at Screening or Day 1 (pre-dose), on Day 1 at 1 hour and 6 hours post-dose, and on Day 7.

ECG results (heart rate, PR, QRS, QT, QTcF, RR) will be summarized and listed for each treatment group by visit. Change from baseline to each scheduled post-dose time point will also be summarized. ECG overall interpretation will also be listed.

### *3.6.6 SARS-CoV-2 Testing*

SARS-CoV-2 testing may be performed at Screening if needed. All available data will be listed.

## **4 DATA SAFETY MONITORING BOARD**

A Data Safety Monitoring Board (DSMB) will monitor the safety of subjects over the course of the study. The DSMB will meet once or more during the subject enrollment period to examine the unblinded accumulated safety data. Subjects, investigators, site staff and in general all personnel directly involved in the conduct of the study will remain blinded to the subjects' treatment assignment until the completion of the study.

Details related to the DSMB responsibilities, authorities, and procedures will be documented in a DSMB charter which will be finalized prior the first subject being enrolled in the study.

## **5 ANALYSIS TIMING**

### **5.1 Interim Analysis**

No formal interim analysis is planned.

### **5.2 Pre-Final Analysis**

After the database is locked and exclusions from analysis populations have been finalized, the randomized treatment assignments will be unblinded and the pre-final analysis will be generated.

### **5.3 Final Analysis**

After all comments on the pre-final analysis have been resolved and the study database is declared final, the final analysis will be generated. If there were no changes to the pre-final analysis or the study database, the pre-final TFLs may be considered final.

[figure not shown]
## **6 CHANGES FROM PROTOCOL-SPECIFIED STATISTICAL ANALYSES**

[figure not shown]
Laboratory assessments will be summarized by incidence of abnormalities instead of change from baseline values at each visit.

[figure not shown]

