7 ENDPOINTS

7.1 Primary Endpoint

The primary endpoint is the safety of ADX-629, determined by evaluation of the following:

- AEs;
- Safety laboratory tests (including chemistry, hematology, coagulation parameters, and urinalysis);
- Vital signs (including heart rate, blood pressure, respiratory rate, temperature, and oxygen saturation);
- Physical examinations; and
- 12-lead ECGs.

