9.2.2 Analysis of Safety

AEs will be classified according to the Medical Dictionary for Regulatory Activities (MedDRA) and will be presented by counting the number of subjects reporting each event by treatment. The number (percentage) of subjects reporting TEAEs and SAEs for each preferred term will be tabulated by system organ class (SOC), by SOC and severity, and by SOC and relationship to the study drug. If more than 1 event occurs with the same preferred term for the same subject, the subject will be counted only once for that preferred term using the most severe or related occurrence for the summary by severity or relationship to study drug, respectively.

If specific AEs occur in a sufficient number of subjects, an exposure-response model may be developed as a secondary analysis.

Clinical laboratory values (excluding efficacy laboratory parameters) will be summarized by treatment arm, including changes from baseline at each visit.

Vital signs and change from baseline in vital signs will be summarized descriptively at each visit by treatment arm.

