#### 2.2.4 *Sample Size Determination*

Approximately 30 subjects will be randomized in a 2:1 ratio to 1 of 2 treatment groups: ADX-629 or placebo, both with standard of care treatment for COVID-19. This clinical trial is exploratory in nature and is not formally powered.

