### *3.6.2 Clinical Laboratory Tests*

All standard blood tests will be analyzed by the local laboratory as specified in the Schedule of Procedures (Appendix A). A list of laboratory tests to be performed is included in Appendix B.

The incidence of abnormalities (as defined by normal ranges) after the first dose of study drug will be summarized with counts and percentages of subjects for each treatment group.

Post-baseline clinically significant lab results will also be summarized with counts and percentages of subjects for each treatment group.

All abnormal lab data will be listed.

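### The SAP drops the protocol's by-visit laboratory change-from-baseline summary, leaving no group-level view of the size or timing of laboratory change and none of movement within the normal range

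*SAP*

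**What the plan says.** Protocol 7.1 makes laboratory tests part of the primary endpoint: "Safety laboratory tests (including chemistry, hematology, coagulation parameters, and urinalysis". They stand beside adverse events, vital signs, physical examinations and ECGs.

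Protocol 9.2.2 sets out their analysis: "Clinical laboratory values (excluding efficacy laboratory parameters) will be summarized by treatment arm, including changes from baseline at each visit".

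SAP 6 replaces it: "Laboratory assessments will be summarized by incidence of abnormalities instead of change from baseline values at each visit". SAP 3.6.2 then gives three outputs:

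- a count against the reference range: "The incidence of abnormalities (as defined by normal ranges) after the first dose of study drug will be summarized with counts and percentages of subjects";
- a second count: "Post-baseline clinically significant lab results will also be summarized with counts and percentages of subjects for each treatment group";
- a listing: "All abnormal lab data will be listed".

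No by-visit table, change from baseline or baseline-to-worst shift table remains for laboratory data. SAP 3.6.3 and 3.6.5 keep change from baseline for vital signs and ECG intervals. On size, SAP 2.2.4 says "Approximately 30 subjects will be randomized in a 2:1 ratio to 1 of 2 treatment groups: ADX-629 or placebo" and "This clinical trial is exploratory in nature and is not formally powered".

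**The concern.** Most of the laboratory panel is measured on a continuous scale. A count against the normal range treats a result just above the limit like one far above it. It shows nothing when a value moves but stays in range. A single post-dose count also removes timing, so an early transient rise and a sustained one look the same.

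The trial's primary question is safety, and it has only about 10 placebo subjects. A modest shift in transaminases, creatinine or blood counts may not appear as a difference in proportions, although the values that could show it have been collected. Vital signs and ECG intervals keep the summary that laboratory tests lose, and the readable text does not say why.

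**Working it through.** **1. What each kind of change leaves in the planned outputs**

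| Change in a subject | Where it appears under the SAP |
|---|---|
| Clinically significant | Clinically significant count. It is also reported as an adverse event (Protocol 8.1), graded by CTCAE 5.0 (8.1.3) and tabulated by maximum severity if treatment-emergent (SAP 3.6.1) |
| Out of range, not clinically significant | Range count and listing |
| Within range, not clinically significant | No planned output |

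No output in the table gives mean or median values or changes by arm, or changes by visit.

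**2. Size of the loss, as an illustration**

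The documents give no laboratory effect size, SD, alpha or test, so there is no planned figure to reproduce.

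From the documents:
- About 30 subjects at 2:1, so 30 × 2/3 = 20 and 30 × 1/3 = 10.
- Four laboratory visits after Day 1 that all subjects share: Days 7, 13, 22 and 28 (Protocol 6.3).

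Assumed:
- Normal values with SD 1 and the same shift δ in every treated subject.
- Within-subject correlation 0.6 (between-subject variance 0.6, residual 0.4).
- 5%, 15% or 30% of results abnormal without drug.
- Two-sided 5% level, no dropout.

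*Baseline-adjusted change at one visit.* The residual SD is √(1 − 0.6²) = 0.8. The noncentrality is (δ/0.8) × √(20 × 10/30) = (δ/0.8) × 2.582, on 27 df.
- δ = 0.75: 0.9375 × 2.582 = 2.42, detection 65% (simulation 61 to 64%).
- δ = 0.5: 0.625 × 2.582 = 1.61, detection 34% (simulation 32 to 35%).

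*Raw change at one visit*, the quantity the protocol would tabulate. The SD is √[2(1 − 0.6)] = 0.894, on 28 df.
- δ = 0.75: noncentrality 2.17, detection 55%.
- δ = 0.5: noncentrality 1.44, detection 29%.

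*Any abnormal result over four visits, Fisher's test.* With c the normal quantile that leaves the chosen abnormal rate above it, P(any) = 1 − E[Φ((c − δ − u)/√0.4)⁴], where u ~ N(0, 0.6). At a 5% rate and δ = 0.75 this is about 13% on placebo and 39% on drug, or 1.3 of 10 against 7.8 of 20 subjects. Ranges over repeated simulations:

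| δ | 5% abnormal | 15% | 30% | One visit, baseline-adjusted |
|---|---|---|---|---|
| 0.75 | 21–23% | 28–29% | 33–35% | 61–65% |
| 0.5 | 6–7% | 12–14% | 15–19% | 32–35% |

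Part of the gap is Fisher's conservatism. With no drug effect it rejects in about 2 to 3% of trials, against 5 to 6% for the adjusted analysis.

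**3. How far this depends on the assumptions**

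- *Abnormality rate at a single visit.* The efficiency of the cut relative to the continuous value is φ(c)²/[p(1 − p)]. At p = 5%, c = 1.645 and φ(c) = 0.1031, so 0.01064/0.0475 = 22%. It is 34% at p = 10%, 54% at 25% and 64% at 50%.
- *Number of visits.* For a 1 SD shift with nine visits, correlation 0.5 and a 10% rate, the count reaches 63% against 71% for change at the last visit. The relation is not monotone. At a 50% rate with nine visits almost everyone is abnormal at some point, and the count detects 6% against 69%.
- *Pattern of harm.* If only 15 to 25% of treated subjects react, with a 3 to 6 SD rise and 5% abnormal at baseline, the count detects 4 to 14% and one-visit change 7 to 21%. Both are weak.

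**The case against.** The case for the SAP has real substance.

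- **Size is not wholly discarded.** A reader might infer that the SAP throws away the size of every change. It does not. Abnormal values are listed by subject, clinically significant results have their own count, and they enter the adverse event tables with a severity grade. This stands.
- **The loss is not a planned power loss.** A reader might infer that most of the ability to detect a drug shift is gone. No laboratory test is planned, the trial is exploratory, and step 3 shows that the loss ranges from slight to nearly complete. This stands too. The detection rates are only an index of what a descriptive table could reveal.
- **The comparator matters.** Averaging four post-baseline visits with baseline adjustment would raise detection to about 88% at 0.75 SD, but neither document plans that analysis for laboratory values. One-visit change is the fair comparison.
- **The change is declared.** SAP 6 is the right place for it. Only the absence of a reason in the readable text can be noted.
- **Local laboratories offer a possible ground.** Tests are run locally and may come from routine care (Protocol 8.7), and a range-based count avoids unit problems. However, the ranges themselves may differ by site. The count also has no condition that the value was normal at baseline. It depends on how often a subject is tested: nine laboratory visits after Day 1 for a subject who stays an inpatient, four for an outpatient.

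None of this restores a group-level summary of magnitude or timing, or makes within-range movement visible.

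**Conclusion.** The concern holds in a limited form. For one component of the primary safety endpoint, the SAP removes the only planned group-level summary of magnitude and timing, and the remaining outputs do not replace it. Individual large abnormalities remain visible.

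Under a uniform shift, correlation 0.6 and 5 to 30% abnormal, one-visit adjusted change detects roughly two to three times as many 0.75 SD shifts as the four-visit count (61 to 65% against 21 to 35%). Unadjusted change still does better, at 55%. These ratios rest entirely on assumed inputs and shrink when a minority of subjects react. The documents do not support a claim that the safety analysis is blind to laboratory harm, or that a fixed share of power is lost. This is an inexpensive improvement that should be made, not a flaw that invalidates the trial.

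**What to change.** Delete the replacement in SAP 6 and amend SAP 3.6.2 to restore a descriptive summary of value and change from baseline, by arm, for chemistry, hematology and coagulation analytes at Days 7, 13, 22 and 28. Convert results to common units, and express enzymes and creatinine as multiples of the local upper limit of normal. Keep the incidence and clinically significant counts as a supplement.

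Two additions are optional: a baseline-to-worst shift table, and arm differences with 95% confidence intervals. The intervals go beyond Protocol 9.2.2 and, over many analytes and four visits, should be labelled descriptive. If the inpatient-only visits and urinalysis are left out of the change tables, SAP 6 should say so and why.

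The cost is SAP wording, unit and upper-limit standardisation across the local laboratories of about 3 sites, and one more set of tables to read. No new visits, samples or subjects are needed.

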## **7 PROGRAMMING SPECIFICATIONS**

Analyses will be performed using SAS® version 9.4 or higher. Detailed Programming Specifications will be provided in a separate document.

